9.2.1 Populations for Analysis

The full analysis set (FAS) will consist of all consented and randomised patients who receive any amount of the intervention, which will serve as the primary analysis set. A supporting efficacy analysis will be performed for the per-protocol set (PPS), which will exclude all patients with major deviations (e.g., patients who receive an IMP different to the IMP assigned by randomisation; patients who receive <50% of the planned dose; and patients who significantly violate inclusion/exclusion criteria). Randomised but untreated patients will not be included in the efficacy or safety analyses, but will be followed for 30 days to determine between-group comparability in baseline characteristics and outcomes.

A final decision about the classification of protocol deviations and their consequences regarding assignment of patients to analysis populations will be made during the data review meeting prior to the final analyses. All protocol deviations documented during the conduct of the study or identified at the data review process prior to database lock will be reviewed and classified as minor or major and with respect to their significance for the

planned analyses. This classification of protocol deviations is the joint responsibility of the clinical project manager, the study statistician, and Octapharma's responsible medical expert, and will be agreed and documented before the database is locked and the statistical analyses are performed.

The safety analysis population (SAF) will be identical to the FAS. In addition, to ensure that the safety reporting is complete, all haemostatic therapy and SAE data will be collected in cases where consent for remaining in the study cannot be obtained from Canadian sites due to logistical issues (e.g., patient died and a legally authorised representative could not be reached) and REB approval is obtained to collect the information. For Canadian patients who refuse consent, only treatment allocation data will be collected, and patients will not be included in any analyses.

The following subgroups will be analysed: sex (male/female); urgency (elective/non-elective surgery); and complexity (simple/complex surgery [procedures other than isolated ACB, single valve or repair of atrial septal defect]). Moreover, the impact of CPB duration on effectiveness will be evaluated by assessing treatment effect based on CPB duration increments.

Details on the subgroup analyses will be given in a Statistical Analysis Plan.

9.2.2 Efficacy Analysis Plan

Descriptive statistics or frequency tables will be presented for all efficacy data in addition to the inferences performed. Simple tests of comparison will be used to compare endpoints between the two groups. The summary tables and exploratory inferences will be chosen according to the scaling level of the measurements. Frequency tables will be provided for categorical responses and summary statistics for continuous data. The SAP will detail all analyses, including exploratory analyses (e.g., *p*-values and confidence intervals) to be undertaken.

9.2.3 Safety Analysis Plan

Secondary safety endpoints will be analysed analogously to the primary endpoint, presenting point estimates and two-sided 95% CIs in addition to descriptive statistics. Prior to study initiation, the SAP will detail all analyses to be undertaken.

9.2.3.1 Adverse events, including thromboembolic and other events of special interest

AEs will be coded according to the latest Medical Dictionary for Regulatory Activities (MedDRA) version as specified in the Data Management Plan. The analysis will focus on treatment-emergent adverse events (TEAEs), i.e., AEs that started or worsened after start of infusion with IMP.

All TEAEs, related TEAEs (i.e., AEs unlikely, probably or possibly related to the IMP) and serious TEAEs will be summarised and tabulated according to primary system organ class and preferred term. TEAEs leading to death and TEAEs resulting in withdrawal from the study will be tabulated using frequency tables if a reasonable number of events of this type are observed.

Analogous frequency tables for TEEs (identified using MedDRA SMQs) and composite events will be provided separately.

Patient listings will be provided for patients with SAEs, TEEs, AEs leading to withdrawal from the study and AEs leading to death. Listings for non-treatment-emergent AEs, e.g., for patients enrolled but not randomised will be provided separately.

9.2.3.2 Mortality

The number of patients who died will be summarised. A possible difference between treatment groups will be estimated by a risk ratio with 95% CI. Kaplan-Meier estimates for the time to death distribution will be calculated and graphically presented if a sufficient number of cases have been registered.

Routine laboratory data

All laboratory values will be classified as normal or abnormal according to the laboratories' normal ranges and indicated as clinically significant or not clinically significant by the Investigator. The following approaches will be taken for each laboratory parameter for the statistical analysis:

- Quantitative data will be examined for trends using descriptive analysis (number of patients, number of missing values, mean, SD, median, quartiles, minimum, maximum) of actual values at each scheduled time point and changes from baseline to each scheduled time point. Mean concentration versus time profiles will be plotted for quantitative data
- Qualitative data based on reference ranges will be described according to the categories (i.e., low, normal, high)
- Shift tables illustrating changes with respect to the laboratories' normal ranges between baseline and a defined scheduled time point. Scatterplots between scheduled time points of lab values with normal ranges will be used for visual illustration.
- Number and frequency of patients with clinically significant laboratory values. A separate patient listing will be provided

9.2.4 Handling of Missing Data

In general, missing data will not be imputed. Due to the nature of the study, important variables are expected to have few missing data. In addition to presentation of the primary and secondary endpoints for different analysis sets, further multiple imputation methods may be used to impute missing values. Technical details will be described in the Statistical Analysis Plan.

9.3 Randomisation, Stratification and Code Release

Eligible patients will be randomly assigned to receive either *Octaplex* or FP. Randomisation lists using a permuted-block, randomisation scheme (stratified by site) will be prepared by the biostatistician. Sealed randomisation envelopes based on the randomisation lists will then be provided to the blood banks/pharmacies of the participating centres who will be responsible for providing the IMP.

Patients will be identified using a sequential numbering system within the centre. Randomisation will then be performed in sequential order of the patient IDs.

9.4 Interim Analysis

An administrative unblinded interim analysis will be carried out by an independent statistician when approximately 200 patients have been randomised and treated. Unblinded information will be communicated only to the IDSMC. Possible outcomes of this analysis and recommendations to the sponsor are:

- The study will be stopped for futility. The decision to stop for futility is non-binding.
- The sample size will be re-estimated by the independent statistician.

Patient recruitment will continue during the conduct of the interim analysis. The study cannot be stopped for efficacy at the interim analysis.

The sample size re-estimation will be based on the evaluation of the conditional power, calculated as described in section 7.3 of [94] making use of the observed response rates at the time of the interim analysis and inverse normal combination test statistic with equal weights given by

$$(\Phi^{-1}(1 - p_1) + \Phi^{-1}(1 - p_2))/\sqrt{2},$$

where p_1 and p_2 denote the p-values for testing the non-inferiority null hypothesis for the first and the second stage of the trial, respectively. The aspired conditional power used for the new intended sample size will be 90%.

A 20% drop-out rate will be added to the re-estimated sample size of evaluable patients to receive the number of patients to be enrolled in the second stage.

The minimum number of patients for the second stage is 210 evaluable subjects (even if the re-estimated sample size is below this number) or 263 including the possible dropouts (+20%). The sample size for the second stage cannot exceed 1250 patients (dropouts included). If the drop-out adjusted re-estimated sample size exceeds this threshold, the IDSMC may recommend to either stop the trial for futility or to enrol the maximum number of 1250 patients.

In addition, the IDSMC will review selected unblinded summary statistics every time 100 patients have completed the study (**Section 8.6**).

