3.3.1.5 Recruitment and Informed Consent

This is a pragmatic trial that compares two coagulation factor replacement therapies that are currently routinely used for the study indication in multiple regions globally and in various settings. It is not expected that participating in the trial will pose any risks to patients.

All patients ≥ 18 years old undergoing cardiac surgery with CPB at the study centres will be offered the chance to participate in the study prior to their surgery. Voluntarily given, written, informed consent will be obtained from the patient before the study procedures start. Once consent has been obtained and the patient enrolled into the study, eligibility according to inclusion criteria 1 and 4 (i.e., patients ≥ 18 years old, undergoing any index cardiac surgery employing CPB, who have provided informed consent) and the exclusion criteria will be confirmed. If screening is performed before the day of surgery, exclusion criterion 3 (i.e., severe right heart failure [clinical diagnosis \pm echocardiography]) will be rechecked on the day of surgery².

Only patients who require coagulation factor replacement therapy during surgery will be randomised, receive study drug, and undergo the proceeding visits and assessments. When the first order for PCC or FP is received by the blood bank/pharmacy while the patient is in the operating room, the blood bank/pharmacy technologist will confirm patient eligibility with the clinical team. Following confirmation of eligibility, the technologist will randomise the patient to PCC or FP according to the randomisation and dosing schedule.

²In Canada, informed consent will be obtained after randomisation, in accordance with Article 3.7A of the 2018 Tri-Council Policy Statement on the Ethical Conduct for Research Involving Humans.

Randomisation (1:1) will continue until at least 410 evaluable patients are obtained (205 patients per group).

3.3.1.6 *Blinding*

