9.1 Determination of Sample Size

The analysis of the primary efficacy endpoint will involve comparison of haemostatic treatment response to IMP, defined as 'effective' if no additional haemostatic intervention, such as administration of any systemic haemostatic agents (including platelets, cryoprecipitate, fibrinogen concentrate, activated recombinant factor VII, other coagulation factor products or a second dose of IMP) or any haemostatic interventions (including surgical re-opening for bleeding) is required from 60 minutes to 24 hours after initiation of the first dose of IMP.

Patients categorised as having an 'ineffective' haemostatic treatment response to IMP, due to requiring administration of any haemostatic intervention, including a second dose of IMP, in the time window from 60 minutes to 24 hours after initiation of the first IMP dose, will be considered as treatment failures.

Of the more than 100 patients studied in the FARES pilot study, approximately 75% of patients in the PCC group and 65% in the FP group demonstrated haemostatic treatment response from 60 minutes to 24 hours after initiation of the first IMP dose [58]. Using a more conservative estimate of 70% versus 65%, it is estimated that 410 patients will be required to demonstrate non-inferiority with a one-sided α of 0.025, power of $\geq 90\%$ and non-inferiority margin of 0.10 when using a Farrington-Manning score test.

It is anticipated that up to 20% of randomised patients may not meet administration criteria (based on objective Bleeding Severity Scale and INR) due to cessation of haemorrhage between randomisation and delivery of IMP to the operating room and therefore will not receive the therapy.

An administrative unblinded interim analysis will be carried out after 200 evaluable patients have been randomised and treated and will be used to re-estimate the sample size or stop for futility (non-binding) (**Section 9.4**). Patient recruitment will continue during the conduct of the interim analysis. The sample size in the second stage is limited to 210–800 evaluable patients. Accounting for drop-outs as described above, the total sample size will range between 513–1250 if the study is not stopped for futility at the interim (see table below).

	Stage 1	Stage 2 – Minimum	Stage 2 – Maximum	Total - Maximum
Evaluable patients	200	210	800	1000
Sample size including 20% dropouts	250	263	1000	1250

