## 7.4. Interim Analysis

An administrative unblinded interim analysis will be carried out when approximately 50% of the target number of evaluable patients have been randomised and treated (100 evaluable patients in each treatment group) by an independent statistician. Unblinded information will be communicated only to the IDSMC. Possible outcomes of this analysis are:

- The study may be stopped for futility after an evaluation of the sample size calculation at the interim analysis.

- The sample size will be re-estimated by the independent statistician.

The study cannot be stopped for efficacy at the interim analysis.

The sample size re-estimation will be based on the evaluation of the conditional power, calculated as described in section 7.3 of [15] making use of the observed response rates and inverse normal combination test statistic with equal weights given by

$$(\Phi^{-1}(1 - p_1) + \Phi^{-1}(1 - p_2))/\sqrt{2},$$

where  $p_1$  and  $p_2$  denote the p-values for testing the non-inferiority null hypothesis for the first and the second stage of the trial, respectively. The aspired conditional power used for the new intended sample size will be 90%.

A 20% dropout rate will be added to the re-estimated sample size of evaluable patients to receive the number of patients to be enrolled in the second stage.

The minimum number of patients for the second stage is 210 evaluable subjects (even if the re-estimated sample size is below this number) or 263 including dropouts. The sample size for the second stage cannot exceed 1250 patients (dropouts included). If the dropout adjusted re-estimated sample size exceeds this threshold, the IDSMC may recommend to either stop the trial for futility or to enrol the maximum number of additional 1250 patients.

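### The interim sections describe the drop-out adjustment as adding 20%, but every stated figure divides by 0.8; read literally, the rule enrols 4% too few for re-estimates between the stage-two limits

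*Protocol*

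**What the plan says.** Protocol 9.1 sets the base size: "it is estimated that 410 patients will be required to demonstrate non-inferiority with a one-sided α of 0.025", with at least 90% power. It assumes response rates of 70% on PCC and 65% on FP, and a "non-inferiority margin of 0.10 when using a Farrington-Manning score test". It expects up to 20% of randomised patients to go untreated. Its table converts evaluable to enrolled numbers as 200 to 250, 210 to 263, 800 to 1000 and 1000 to 1250. The total is given as 513 to 1250. SAP 4.2 repeats the table and the range.

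Protocol 9.4 gives the rule to apply after the interim analysis: "A 20% drop-out rate will be added to the re-estimated sample size of evaluable patients to receive the number of patients to be enrolled". It then sets the stage-two minimum at 210 evaluable patients, "or 263 including the possible dropouts (+20" per cent, as the label reads. SAP 7.4 carries the same rule, "A 20% dropout rate will be added to the re-estimated sample size of evaluable patients", and the same minimum of 263, without the plus-20% label. The target conditional power is 90% in both documents.

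Protocol 3.3.1.5 adds an overall recruitment rule: "Randomisation (1:1) will continue until at least 410 evaluable patients are obtained (205 patients per group").

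**The concern.** Taken at face value, adding 20% means multiplying by 1.20. The drop-out assumption is stated as a share of randomised patients, so the conversion that returns the required evaluable number is division by 1 − 0.20. The two operations differ, and Protocol 9.4 sets the wording of one beside a figure produced by the other.

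The re-estimate can fall anywhere from 210 to 800 evaluable patients, and the documents give enrolled stage-two numbers only for those two end points. For any value in between, the instruction is the sentence about adding 20%. If it were followed literally, stage two would be expected to yield fewer evaluable patients than the conditional-power calculation had just called for.

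**Working it through.** **Inputs.** One-sided α 0.025, power 90%, rates 0.70 and 0.65, margin 0.10, loss of up to 20% of randomised patients, stage-two limits of 210 and 800 evaluable (Protocol 9.1). Stage one of 200 evaluable, equal-weight inverse normal combination, critical value 1.96, target conditional power 90% (Protocol 9.1, 9.2 and 9.4; SAP 4.2, 7.4 and 10.2).

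**Base size.** With unpooled variances, n per arm = (1.960 + 1.2816)² × (0.70×0.30 + 0.65×0.35) / 0.15² = 10.507 × 0.4375 / 0.0225 = 204.3, so 205 per arm and 410 in total. The Farrington-Manning formula with restricted estimates gives 204.4, again 410, with power 90.1% at 205 per arm. The plan's figure is reproduced.

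**Inflated figures.**

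| Evaluable n | Stated | n / 0.8, rounded up | n × 1.2 |
|---|---|---|---|
| 200 | 250 | 250 | 240 |
| 210 | 263 | 263 | 252 |
| 410 | 513 | 513 | 492 |
| 800 | 1000 | 1000 | 960 |
| 1000 | 1250 | 1250 | 1200 |

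All five stated figures match division and none matches multiplication.

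**Size of the difference.** Multiplying by 1.2 and then losing 20% leaves 1.2 × 0.8 = 0.96 of the target. With the stated 263 kept as a floor:

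| Re-estimate | Literal rule | n / 0.8 | Evaluable under literal rule at 20% loss |
|---|---|---|---|
| 210 | 263 (floor) | 263 | 210.4 |
| 219 | 263 (1.2 × 219 = 262.8) | 274 | 210.4 |
| 300 | 360 | 375 | 288 |
| 400 | 480 | 500 | 384 |
| 600 | 720 | 750 | 576 |

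**When the wording can matter.** Let z₁ be the stage-one statistic. Stage two must exceed c = 1.960×√2 − z₁ = 2.772 − z₁. If the observed effect continues and the variance is similar in both stages, the expected stage-two statistic is z₁√(n₂/200). For 90% conditional power this must equal c + 1.2816, so n₂ = 200 × ((4.053 − z₁)/z₁)².

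- n₂ = 210 gives z₁ = 4.053/(1 + √1.05) = 2.00.
- n₂ = 800 gives z₁ = 4.053/3 = 1.35.
- At the planned rates the expected z₁ is 0.15/√(0.4375/100) = 2.27, where n₂ = 200 × (1.783/2.27)² ≈ 123, so the minimum governs.

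**Effect on conditional power.** With 0.96 of the required n₂, conditional power is Φ((c + 1.2816)√0.96 − c). For a re-estimate of 400, z₁ = 4.053/(1 + √2) = 1.679 and c = 1.093. The argument is 2.374 × 0.9798 − 1.093 = 1.234, so conditional power is 89.1%. At z₁ = 1.5 it is 89.1%, and at z₁ = 2.0 it is 89.3%.

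**The case against.** The strongest reply is that the documents already show what the phrase means. The rule speaks of a drop-out rate, and Protocol 9.1 defines that rate on randomised patients, which implies division. The next sentence of 9.4 applies the phrase to 210 and arrives at 263, which is 210/0.8. The tables give four conversions, all by division. A statistician facing a re-estimate of 400 has worked examples at both ends of the range. This stands as evidence of intent, and for that reason a shortfall is a possible outcome of the wording and not an established one. It does not remove the contradiction between words and figure inside one section. The SAP rule has no worked label beside it except the bare 263.

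A reader might go further and infer that the rule breaks the plan's own minimum of 210 evaluable patients, since 210 × 1.2 = 252 and 252 × 0.8 = 201.6. The documents do not support that. Protocol 9.4 and SAP 7.4 both state the minimum as 263 enrolled, and 263 × 0.8 = 210.4. Nor would 800 become 960, because the table states 1000.

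The 20% is also an upper bound. Multiplying by 1.2 delivers the full target if the loss is 1 − 1/1.2 = 16.7% or less, so the 4% shortfall is the worst case within the plan's assumption. This too stands.

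The requirement for at least 410 evaluable patients gives less protection than it seems to. It equals 200 + 210, the minimum design, and is not tied to a larger re-estimate.

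**Conclusion.** The point holds as a small inconsistency between wording and arithmetic. The verbal rule in Protocol 9.4 and SAP 7.4 says to add 20%; all the stated figures divide by 0.8, and division is what the drop-out assumption requires. The stated sample sizes are correct.

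For re-estimates between 210 and 800 evaluable patients, a literal reading would enrol about 4% too few (slightly less just above 210, where the 263 floor helps) and lower conditional power from 90% to about 89%. This assumes that the full 20% drop out, that enrolment stops at the converted number, and that the interim effect continues. It can arise only for a stage-one statistic of about 1.35 to 2.00; at the planned rates the expected value is 2.27 and the wording has no effect. Type I error, the test and the estimand are untouched.

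The stage-two cap of 1250 in Protocol 9.4 and SAP 7.4, against 1000 in the tables, is a separate matter and plays no part here.

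**What to change.** In Protocol 9.4 and SAP 7.4, replace the sentence on adding a drop-out rate with a statement that the re-estimated number of evaluable patients is divided by 0.80 and rounded up to give the number to enrol in stage two. Delete the plus-20% label after 263 in Protocol 9.4. If the re-estimation has already been done, which the documents do not say, record which conversion was used.

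The cost is one sentence in each document and one deleted label. No stated sample size, test or study procedure changes.

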The study is split in two stages. In the first stage, randomisation (1:1) will continue until 200 evaluable patients are obtained. Then, an administrative unblinded interim analysis will be carried out to re-estimate the sample size or stop for futility (non-binding) if necessary. The sample size in the second stage is limited to 210–800 evaluable patients. Accounting for 20% dropouts, the total sample size of the study will range between 513–1250 if the study is not stopped for futility at the interim.

Subject/Patient Selection Criteria:**Inclusion Criteria:**

1. Adult (≥ 18 years old) patients undergoing any index cardiac surgery employing CPB
2. Coagulation factor replacement with PCC or FP ordered in the operating room for:
 - a. Management of bleeding, or
 - b. Anticipated bleeding in a patient who has been on-pump for >2 hours or has undergone a complex procedure (e.g., aortocoronary bypass [ACB] plus aortic valve replacement)
3. Coagulation factor deficiency, either known to exist (e.g., as indicated by elevated EXTEM clotting time [CT] or INR) or suspected based on the clinical situation
4. Patients who have given written informed consent¹

Exclusion Criteria:

1. Undergoing heart transplantation, insertion or removal of ventricular assist devices (not including intra-aortic balloon pump [IABP]) or repair of thoracoabdominal aneurysm
2. Critical state immediately before surgery with high probability of death within 24 hours of surgery (e.g., acute aortic dissection, cardiac arrest within 24 hours before surgery)

¹ In Canada, informed consent will be obtained after randomisation, in accordance with Article 3.7A of the 2018 Tri-Council Policy Statement on the Ethical Conduct for Research Involving Humans.

Name of Sponsor/Company: Octapharma AG	
Name of Investigational Product: Octaplex	Protocol Identification Code: LEX-211
Name of Active Ingredient: Prothrombin complex concentrate, human	Date of Final Protocol: 25-Aug-2023

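### The interim-analysis sections cap stage 2 at 1250 randomised patients, but the sample-size sections cap it at 1000, with 1250 as the limit for the whole trial

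*Protocol*

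**What the plan says.** **Sample-size text.** Protocol 9.1 states: "The sample size in the second stage is limited to 210–800 evaluable patients". The synopsis and SAP 4.2 give the same limit. Protocol 9.1 continues that "the total sample size will range between 513–1250 if the study is not stopped for futility at the interim", and the synopsis (Number of Patients) and SAP 4.2 repeat that range. The tables in protocol 9.1 and SAP 4.2 are identical:

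| | Stage 1 | Stage 2 min | Stage 2 max | Total max |
|---|---|---|---|---|
| Evaluable | 200 | 210 | 800 | 1000 |
| With 20% dropouts | 250 | 263 | 1000 | 1250 |

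**Interim text.** Protocol 9.4 gives the stage-2 minimum as 210 evaluable or 263 with dropouts, as in the table. It then says "The sample size for the second stage cannot exceed 1250 patients (dropouts included"). If the dropout-adjusted re-estimate is above that threshold, "the IDSMC may recommend to either stop the trial for futility or to enrol the maximum number of 1250 patients". SAP 7.4 has the same cap but describes the second option as "to enrol the maximum number of additional 1250 patients".

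**The concern.** The figure 1250 is a trial total in one set of sections and a limit on stage 2 alone in the other. The conflict lies inside each document, so neither can be used to settle the other.

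The interim text is hard to read as meaning the total. In protocol 9.4 the cap names the second stage, follows directly on the stage-2 minimum, and is compared with a quantity which that section defines as the number to enrol in the second stage. In SAP 7.4 the word for patients on top of stage 1 rules out a total.

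The cap is an operative instruction at an unblinded interim. It fixes when the IDSMC must choose between stopping for futility and enrolling the maximum, and it fixes what that maximum is. With two written caps, the choice between them could be made after the data have been seen, which pre-specification is meant to prevent. Protocol 10.4 also requires IRB approval for an increase in the number of patients treated, so the approved maximum has to be unambiguous.

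**Working it through.** **1. Reproduce the plan's figures.** For the base size, protocol 9.1 states: "it is estimated that 410 patients will be required to demonstrate non-inferiority with a one-sided α of 0.025", with rates of 70% vs 65%, margin 0.10 and power of at least 90%. The usual non-inferiority formula for two proportions gives 205 per arm = 410. Farrington-Manning power at 205 per arm is 0.901.

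For dropouts, randomised = evaluable/(1 - 0.20):
- 200/0.8 = 250
- 210/0.8 = 262.5, rounded up to 263
- 410/0.8 = 512.5, rounded up to 513
- 800/0.8 = 1000
- 1000/0.8 = 1250

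Every cell of the table and the minimum total of 513 are reproduced. Reading the 20% as a multiplier does not reconcile the texts: 800 × 1.2 = 960 and 1000 × 1.2 = 1200.

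**2. Apply each cap.**

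| | Stage 2 randomised | Stage 2 evaluable | Total randomised | Total evaluable |
|---|---|---|---|---|
| Sample-size sections | 1000 | 800 | 250 + 1000 = 1250 | 1000 |
| Interim sections, literally | 1250 | 1250 × 0.8 = 1000 | 250 + 1250 = 1500 | 1200 |

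The gap is 250 randomised or 200 evaluable, both for stage 2 and for the trial.

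**3. How often the cap matters.** The plan defines conditional power by a textbook section that is not available here. The following reconstruction uses the stated ingredients (observed rates, equal-weight inverse normal statistic, critical value 1.96, 90% target). Let d be the observed PCC minus FP difference, v = pPCC(1 - pPCC) + pFP(1 - pFP), z1 the Farrington-Manning statistic at 100 per arm, and n2 the evaluable stage-2 size. Then

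CP = Φ( z1 + (d + 0.10)·√((n2/2)/v) - √2 × 1.96 ),

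and the required n2 solves (d + 0.10)·√((n2/2)/v) = √2 × 1.96 - z1 + 1.2816.

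With 1,000,000 simulated interims per scenario:

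| True rates, PCC vs FP | n2 > 800 | n2 > 1000 | Between (trigger differs) |
|---|---|---|---|
| 75% vs 65% | 4.0% | 3.4% | 0.6% |
| 70% vs 65% | 18.0% | 15.9% | 2.1% |
| 65% vs 65% | 45.3% | 41.0% | 4.3% |

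The required n2 reaches 800 and 1000 at observed differences of -0.6 and -1.3 points (FP observed at 60%), -0.9 and -1.5 (65%), and -1.2 and -1.8 (70%). These FP rates are assumptions.

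**4. What the gap is worth if the cap binds and the trial continues.** Take observed FP 65% and PCC 63%, so d = -0.02.
- v = 0.63 × 0.37 + 0.65 × 0.35 = 0.4606.
- The restricted null rates are 0.588 and 0.688, so z1 = 0.08/√((0.588 × 0.412 + 0.688 × 0.312)/100) = 1.183.
- √2 × 1.96 = 2.772.
- Required n2 = 2 × 0.4606 × ((2.772 - 1.183 + 1.2816)/0.08)², about 1186, above both caps.
- At n2 = 800: 0.08 × √(400/0.4606) = 2.358, so CP = Φ(1.183 + 2.358 - 2.772) = Φ(0.769) = 0.78.
- At n2 = 1000: 0.08 × √(500/0.4606) = 2.636, so CP = Φ(1.047) = 0.85.

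Other cases (800 vs 1000 evaluable):
- d = -2 points, FP 60%: 75% vs 83%.
- d = -2 points, FP 70%: 82% vs 88%.
- d = -3 points, FP 65%: 63% vs 71%.

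**The case against.** The strongest reply is that the slip has little statistical effect and an obvious resolution.

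- **Power.** When the same model is carried to the end of the trial, always continuing and with stage 2 held to 210-800 or 210-1000 evaluable, overall power is 99.9% under both caps at 75% vs 65%. It is 98.3% vs 98.4% at the planning rates. A visible difference (82.4% vs 85.9%) appears only at 65% vs 65%, which is not a planning scenario in the documents.
- **Type I error.** It does not depend on the cap, and futility is non-binding.
- **Intent.** Every maximum given in evaluable patients agrees (800 and 1000), and 1250 equals the total-maximum cell. The trial total was probably carried into the interim sections by mistake.
- **Frequency.** The 18% is how often the 800 limit is exceeded, whichever cap is right. The trigger itself differs in only 0.6% to 4.3% of trials. Where 800 is exceeded, conditional power at 800 is often below 50% (37%, 51% and 66% of such trials in the three scenarios), so stopping is a real option.

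All of this stands as a statement of size, and the IDSMC charter, which is not available here, may be more specific. None of it removes the conflict. A carried-over total is an inference, and the SAP's wording goes against it. Where both caps bind and the trial continues, one text has 1000 more patients enrolled and the other 1250.

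**Conclusion.** The concern holds. Both current documents state two incompatible stage-2 caps, 250 randomised (200 evaluable) patients apart, so the maximum trial size is 1250 or 1500 depending on the section read. The table arithmetic is correct. The error is the use of 1250 as a stage-2 limit in the interim sections.

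The statistical consequences are limited. Type I error is unaffected, the futility trigger differs in about 2% of trials at the planning rates, and overall power there changes by about 0.1 point. The practical consequence is larger: in the roughly 16% of trials at the planning rates where both caps would bind, the authorised enrolment is undefined if the trial continues. In the -2 and -3 point examples the two sizes differ by about 6 to 9 points of conditional power.

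The count discrepancy rests on the documents alone. The percentages rest on the reconstructed conditional-power formula, 100 evaluable per arm at the interim, and the assumed true or observed rates shown. It should be corrected because it is a wrong limit in a decision rule, not because it threatens the validity of the test.

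**What to change.** State one stage-2 cap and one total cap, each in evaluable and randomised patients, in identical words in the synopsis, protocol 9.1 and 9.4, and SAP 4.2 and 7.4.

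The version consistent with both tables and the 513-1250 range is 800 evaluable/1000 randomised for stage 2 and 1000 evaluable/1250 randomised in total. On that reading, change 1250 to 1000 wherever protocol 9.4 and SAP 7.4 refer to stage 2, including the SAP's option to enrol 1250 further patients.

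If the sponsor confirms that 1250 randomised in stage 2 was intended, correct the 210-800 limit, both tables and the total range instead. The maximum then becomes 1500 randomised (1200 evaluable).

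SAP version 5.0 is dated 28 October 2024 and completion was planned for the fourth quarter of 2024, so the interim may already have taken place, although the documents do not say so. If it has, add a short note recording the cap that the independent statistician and the IDSMC applied. The cost is a wording change in two documents plus that note. The design and the analysis do not change.
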